The Sponsor has initiated the “parent” studies (Study ATYR1940-C-003 and ATYR-C-004) to this extension study. Study ATYR1940-C-003 is entitled “An Open-Label, Inpatient Dose-Escalation Study to Evaluate the Safety, Tolerability, Immunogenicity, and Biological Activity of ATYR1940 in Patients With Early Onset and Other Pediatric Onset Facioscapulohumeral Muscular Dystrophy” and is being conducted in the US and EU. Study ATYR1940-C-004 is entitled “An Open-Label, Inpatient Dose Escalation Study to Evaluate the Safety, Tolerability, Immunogenicity, and Biological Activity of ATYR1940 in Patients with Limb Girdle and Facioscapulohumeral Muscular Dystrophies”. In both studies, which are being conducted in the US and EU, patients receive ATYR1940 for 12 weeks. Patients who were enrolled in Study ATYR1940-C-004 or in Stage 1 of Study ATYR1940-C-003 and meet the entry criteria may participate in this extension study and continue treatment with weekly ATYR1940. Patients may be treated with ATYR1940 under this protocol until ATYR1940 is approved or its development is discontinued, the study is closed by the Sponsor, or a criterion for study drug discontinuation is met (see Section 6.4.1).

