2.4. Rationale for Current Study

aTyr has shown that: 1) HARS is detected in blood samples from healthy individuals and patients (preclinical work) and in the ATYR1940-C-001 study in blood samples from healthy subjects participating in the study and 2) human skeletal muscle cells release HARS during differentiation, a process that can be regulated by molecules already known to modulate muscle mass and blocked by antibodies to HARS. Furthermore, pharmacological application of ATYR1940 1) alters cytokine and other immune protein release from human primary immune cells, and 2) has immune modulatory activity in rodent models, including a rat model of myopathy. Taken together, HARS is a physiologically relevant modifier of muscle cell biology, and the ATYR1940 nonclinical data suggest that it may have therapeutic effect in patients with inflammatory muscle diseases, including FSHD, by modulating both immune and muscle cell responses.

LGMD2B and FSHD are chronic diseases that will likely require lifelong therapy. In the parent studies, ATYR1940 is administered over a relatively short period of up to 12 weeks (including weekly dosing in the ATYR1940-C-003 study and weekly and twice weekly dosing in the ATYR1940-C004 study). No maximum duration of therapy has been set in the current study, and patients will be allowed to receive treatment with ATYR1940 until ATYR1940 is approved or its development is discontinued, the study is

closed by the Sponsor, or a criterion for study drug discontinuation is met (see Section 6.4.1). The safety and efficacy of longer term exposure to ATYR1940 will be continuously assessed over the course of this extension study.

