Potential planned or unplanned protocol deviations noted during clinical monitoring will be documented by category (i.e., inclusion criteria, exclusion criteria, study drug, safety assessment, lab/endpoint data, visit window, informed consent, prohibited co-medication, overdose/misuse, and other). All deviations will be reviewed, categorized, designated important or not important, and finalized prior to database lock according to the Protocol Deviation Guidance document. Important protocol deviations will be defined as those potentially impacting safety, immunogenicity, or PK/PD assessments.

Relationship to study treatment

AEs related to study treatment will be defined as those entered as possibly, likely, or definitely. None and unlikely will be considered not related to study treatment. If relationship is missing, then the AE will be considered as related to study treatment.

Study day

Study day is defined relative to the date of the first infusion (Week 1) in the current study. For assessments that occur after this visit date, study day is calculated as (assessment date – first infusion date + 1). For assessments that occur prior to first infusion date, study day will be calculated as (assessment date – first infusion date); there is no Study Day 0.

Treatment-emergent adverse event

An AE will be considered to be a treatment-emergent AE (TEAE) for the current study if the AE begins on or after parent study Week 13 visit (Week 13 Day 3 visit for study 004) through the 12-week post-treatment follow-up visit in the current study.

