9.0 Overall Statistical Considerations

All analyses will use SAS® version 9.4 or higher. Summary tables will be organized overall and by disease group, if applicable, for the two Safety populations. All available data will be used in the analyses, and important data will be included in data listings, sorted by site, patient and by visit within patient.

Unless otherwise noted, categorical data will be presented using counts and percentages, with the number of patients in the corresponding Safety population as the denominator for percentages. Percentages will be rounded to one decimal place except 100% will be displayed without any decimal places and percentages will not be displayed for zero counts. Continuous data, unless otherwise noted, are summarized using the number of observations (n), mean, standard deviation (SD), median, minimum, and maximum. Minimum and maximum will be rounded to the precision of the original value. Mean and median will be rounded to 1 decimal place greater than the precision of the original value. The SD will be rounded to 2 decimal places greater than the precision of the original value, up to a maximum of 3 decimal places. No statistical hypothesis testing will be performed for this study.

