9.6 Safety, Tolerability, and Immunogenicity Analyses

9.6.1 Adverse Events, Serious Adverse Events, and Deaths

Adverse events will be collected beginning at informed consent until the end of the study. See Section 6 for definition of TEAE. Adverse events will be coded using MedDRA to assign an SOC and PT to each adverse event and TEAEs will be summarized.

An overall summary of TEAEs including the following categories will be presented for the Safety analysis set by disease group:

- Number of TEAEs reported
- Number and percentage of patients reporting at least one TEAE
- Number and percentage of patients with at least one related TEAE (see definition in Section 6)
- Number and percentage of patients with at least one TEAE leading to study medication withdrawal
- Number and percentage of patients with at least one serious TEAE
- Number of patients with at least one TEAE with fatal outcome

The number and percentage of patients reporting TEAEs will also be summarized for the categories below. Counts will be by patient, not event, and patients will only be counted once within each SOC or PT. Tabulations will be sorted by descending frequency of the number of patients reporting the TEAE for each SOC and by PT within each SOC. Additionally, patients with multiple events within a particular SOC or PT will be counted under the category of their most severe event within an SOC or PT for summaries by maximum grade. Summaries to be provided are the following:

- TEAEs by MedDRA PT
- TEAEs by MedDRA SOC and PT

- Related TEAEs by MedDRA SOC and PT
- TEAEs by MedDRA SOC, PT, and maximum CTCAE grade
- SAEs by MedDRA SOC and PT
- TEAEs leading to study medication withdrawal by MedDRA SOC and PT
- TEAEs with a fatal outcome by MedDRA SOC and PT

TEAEs and non-TEAEs will be listed together.

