14.2 SAFETY, TOLERABILITY, AND IMMUNOGENICITY DATA TABLES

14.2.1 ADVERSE EVENT DATA TABLES

14.2.1.1 Summary of Treatment-Emergent Adverse Events (Safety Population Cumulative)

	EO-FSHD (N = XX) n (%)	FSHD (N = XX) n (%)	LGMD2B (N = XX) n (%)	Total (N = XX) n (%)
Parent and Current Studies: Overall				
Number of TEAEs	xxx	xxx	xxx	xxx
Patients with any TEAE	xx (xx.x)	xx (xx.x)	xx (xx.x)	xx (xx.x)
Patients with any TEAE related ^a	xx (xx.x)	xx (xx.x)	xx (xx.x)	xx (xx.x)
Patients with any TEAE leading to study medication withdrawal	xx (xx.x)	xx (xx.x)	xx (xx.x)	xx (xx.x)
Patients with any serious TEAE	xx (xx.x)	xx (xx.x)	xx (xx.x)	xx (xx.x)
Patients with any TEAE with fatal outcome	xx (xx.x)	xx (xx.x)	xx (xx.x)	xx (xx.x)
Current Study (ATYR1940-C-006) Overall				
Number of TEAEs	xxx	xxx	xxx	xxx
Patients with any TEAE	xx (xx.x)	xx (xx.x)	xx (xx.x)	xx (xx.x)
Patients with any TEAE related ^a	xx (xx.x)	xx (xx.x)	xx (xx.x)	xx (xx.x)
Patients with any TEAE leading to study medication withdrawal	xx (xx.x)	xx (xx.x)	xx (xx.x)	xx (xx.x)
Patients with any serious TEAE	xx (xx.x)	xx (xx.x)	xx (xx.x)	xx (xx.x)
Patients with any TEAE with fatal outcome	xx (xx.x)	xx (xx.x)	xx (xx.x)	xx (xx.x)

Note: FSHD=Facioscapulohumeral muscular dystrophy; LGMD2B=Limb-girdle muscular dystrophy 2B; EO-FSHD=Early Onset Facioscapulohumeral muscular dystrophy

a. "Related" defined as possibly, likely, or definitely.

Note: Percentage based on the number of patients in the Safety population cumulative.

Source: Listing xx.x.xx, Dataset: [NAME], Program: xxxxxx.sas, Output: T_14_2_1_1_XXXXX.rtf, Generated on: DDMMYYYY HH:MM

Page x of y

14.2.1.2 Treatment-Emergent Adverse Events by System Organ Class and Preferred Term (Safety Population Cumulative)

	EO-FSHD (N = XX) n (%)	FSHD (N = XX) n (%)	LGMD2B (N = XX) n (%)	Total (N = XX) n (%)
Parent and Current Studies Overall				
Any treatment-emergent adverse event	xx (xx.x)	xx (xx.x)	xx (xx.x)	xx (xx.x)
System Organ Class 1	xx (xx.x)	xx (xx.x)	xx (xx.x)	xx (xx.x)
Preferred Term 1	xx (xx.x)	xx (xx.x)	xx (xx.x)	xx (xx.x)
Preferred Term 2	xx (xx.x)	xx (xx.x)	xx (xx.x)	xx (xx.x)
...				
System Organ Class 2	xx (xx.x)	xx (xx.x)	xx (xx.x)	xx (xx.x)
Preferred Term 1	xx (xx.x)	xx (xx.x)	xx (xx.x)	xx (xx.x)
Preferred Term 2	xx (xx.x)	xx (xx.x)	xx (xx.x)	xx (xx.x)
...				
System Organ Class 3	xx (xx.x)	xx (xx.x)	xx (xx.x)	xx (xx.x)
...				
Current Study (ATYR1940-C-006) Overall				

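### The adverse event summaries have no time denominator although extension treatment is open-ended, so crude incidence rises with follow-up and disease columns need an adjustment that is not planned

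*SAP*

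**What the plan says.** Section 9.0 of the SAP sets the general rule for categorical data: percentages are formed "with the number of patients in the corresponding Safety population as the denominator for percentages". Section 9.6.1 applies it to the system organ class and preferred term summaries: "Counts will be by patient, not event, and patients will only be counted once within each SOC or PT". Tables 14.2.1.1 to 14.2.1.7 follow this pattern, with columns for EO-FSHD, FSHD, LGMD2B and Total, and the footnote to Table 14.2.1.1 reads "Note: Percentage based on the number of patients in the Safety population cumulative". The one measure that is not a patient count is "Number of TEAEs reported", listed first in section 9.6.1 and shown in Table 14.2.1.1 by disease. It has no time denominator either.

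Time at risk has no common end. Section 2.3 of the protocol says of the parent studies: "In both studies, which are being conducted in the US and EU, patients receive ATYR1940 for 12 weeks". For the extension, section 2.4 says "No maximum duration of therapy has been set in the current study", and section 2.3 says "Patients may be treated with ATYR1940 under this protocol until ATYR1940 is approved or its development is discontinued"; sponsor closure and individual discontinuation criteria also end treatment. For the current study, SAP section 6.0 counts an event as treatment-emergent if it "begins on or after parent study Week 13 visit (Week 13 Day 3 visit for study 004) through the 12-week post-treatment follow-up visit" in the extension.

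Treatment duration in days is summarised separately, by disease and dose level, in Table 14.1.5. Neither the protocol nor either SAP specifies events per patient-time, time to first event, or adverse events by treatment interval.

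**The concern.** The proportion of patients ever affected mixes the event rate with the length of observation. When patients stop at different times, two groups with identical risk show different percentages if their follow-up differs, and any group's percentage rises the longer the study runs. The table sets three disease groups side by side, so readers will compare them.

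Timing also matters for the known risk. Protocol sections 2.3 and 7.5.5.1 say that the generalized infusion-related reactions (IRRs) seen so far came after more than 4 weeks of dosing and only after several doses, and section 7.5.1 allows dose increases after 12 weeks. An ever/never percentage cannot show when in treatment events arise. Generalized IRR has a symptom listing (16.2.9.2) and a withdrawal-reason row (Table 14.1.2), but no incidence row in Table 14.2.1.1.

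**Working it through.** The plan states no event rate, power or calculated sample size for this point, so there is no figure to reproduce. What follows is an illustration, and its rates and follow-up times are assumptions.

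**Inputs.** Constant hazard λ of 0.25 to 2.0 first events per patient-year (assumed). Follow-up T of 24 and 72 weeks (assumed). One year = 52.18 weeks. Up to 24 patients (SAP 3.2); 8 per disease group is assumed (24/3).

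**Which clock.** T is the length of the TEAE window, which is longer than treatment. With a 7-day gap after the parent Week 13 visit, k weekly doses and completed follow-up, the window is 7 + 7(k − 1) + 84 + 1 = 7k + 85 days. For k = 12 this is 169 days (24.1 weeks); for k = 60 it is 505 days (72.1 weeks). So 24 against 72 weeks corresponds to roughly 12 against 60 extension doses.

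**Crude incidence** = 1 − exp(−λT/52.18):

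| λ per year | 24 weeks | 72 weeks | Ratio |
|---|---|---|---|
| 0.25 | 10.9% | 29.2% | 2.69 |
| 0.5 | 20.5% | 49.8% | 2.43 |
| 1.0 | 36.9% | 74.8% | 2.03 |
| 2.0 | 60.1% | 93.7% | 1.56 |

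Risk is the same in both columns of each row; the ratio comes from follow-up alone. At λ = 1.0, 8 patients per group would give about 2.9 against 6.0 affected.

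**With patient-time.** At λ = 1.0, 8 patients over 24 weeks give 8 × 24/52.18 = 3.68 patient-years and 3.68 expected events. Over 72 weeks they give 8 × 72/52.18 = 11.04 patient-years and 11.04 expected events. Both are 1.0 per patient-year.

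**Can the planned tables already give this rate?** Only roughly. Treatment duration is 7(k − 1) + 1 days; the window is 7k + 85.

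| Weekly doses | Duration (days) | Window (days) | Window/duration |
|---|---|---|---|
| 12 | 78 | 169 | 2.17 |
| 24 | 162 | 253 | 1.56 |
| 48 | 330 | 421 | 1.28 |
| 72 | 498 | 589 | 1.18 |

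Dividing the TEAE count by Table 14.1.5 duration would overstate the rate by these factors if events accrue evenly over the window. The overstatement is largest for the shortest treatment.

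**How finely can it be split?** One 12-week interval in 8 patients holds at most 8 × 12/52.18 = 1.84 patient-years. With no events, the exact 95% upper limit is 3.69/1.84 = 2.0 per year. In all 24 patients it is 24 × 12/52.18 = 5.52 patient-years and 3.69/5.52 = 0.67 per year.

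**The case against.** The best defence is that the study is descriptive. The protocol endpoint is incidence of TEAEs, which the tables deliver; no disease comparison is an objective, and no test is planned. Protocol section 9.2.9 allows additional safety analyses, and the data monitoring board reviews safety quarterly. All of this is correct, and it limits the point to what the tables can describe. It does not supply the missing denominator, because the permitted extra analyses are unspecified.

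Some stronger readings are tempting but unsupported:

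- *That the plan reports nothing but patient percentages.* Table 14.2.1.1 also gives the number of TEAEs by disease.
- *That groups cannot be compared at all.* Table 14.1.5 gives treatment duration in matching columns, and listings 16.2.8 and 16.2.9 carry infusion and event dates. An approximate rate can be built, subject to the mismatch between window and duration.
- *That the disease groups have unequal exposure.* No document gives duration by group, and SAP section 3.3 says that dosing guidelines are identical. Open-ended treatment makes imbalance possible, not established.
- *That the two row blocks contrast two study periods.* The parent-plus-current block contains the current-study block, in the same patients. The absence of a parent-only block, despite the separate tabulations promised in Protocol section 9.2.9, is another matter.

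The objection that up to 24 patients cannot support fine splits also stands: disease-by-interval cells would be nearly uninformative.

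**Conclusion.** The point holds in moderate form. The summaries omit time at risk in a study of long-term safety with no fixed treatment length, so crude incidence rises with follow-up at constant risk. Disease columns can be compared only after an adjustment that is not planned. The size, an apparent ratio of about 2.7 to 1.6 for equal risk, depends on the assumed rates of 0.25 to 2.0 per patient-year, a constant hazard and follow-up of 24 against 72 weeks. It would be smaller if groups are followed for similar times.

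A reader might infer that interval rates would settle whether risk persists, rises or falls. They would not do so cleanly. Entrants had already tolerated the drug, and patients with a generalized IRR are discontinued, so a falling rate may reflect depletion of susceptible patients. The addition is worthwhile, but it does not overturn the planned tables.

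**What to change.** Keep the planned tables and add the following to Table 14.2.1.1, by disease and total:

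- **Patient-years at risk**, from the start of the TEAE window to the first event of that category or the end of the window. Off-drug follow-up is included, and a footnote should say so.
- **Events per patient-year**, over the whole window rather than time to first event.
- **First-event incidence per patient-year** with an exact Poisson 95% confidence interval, for any TEAE, related TEAEs, serious TEAEs, TEAEs leading to withdrawal of study drug, and generalized IRR.

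For generalized IRR and withdrawal, use extension time only. Under Protocol sections 5.1 and 5.2, entrants completed parent treatment without meeting a discontinuation criterion, so parent time is event-free by selection and would dilute these two rates.

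Add 12-week treatment intervals for the Total column only, with the number of patients at risk in each. Note that later intervals contain only patients who have tolerated treatment. SAP section 9.5.1 already uses 12-week increments for exposure.

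The cost is some extra programming from dates already collected. With up to 24 patients the intervals will be wide, so the rates should be labelled descriptive and not used for formal comparison.

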3.2. Study Endpoints

3.2.1. Safety and Tolerability Endpoints

The safety and tolerability endpoints of this study are:

- Incidence of TEAEs and serious adverse events (SAEs) overall and by intensity.
- Changes from baseline in:
 - Safety laboratory test results.
 - ECG findings.
 - Vital signs measurements.
 - Pulmonary evaluations (PFTs and pulse oximetry).
- Incidence and level of ADA titers and Jo-1 Ab levels.
- Exploratory characterization of immune response to ATYR1940.

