9.2.8. Safety Analysis

9.2.9. Safety and Immunogenicity Analyses

Safety evaluations will be based on the incidence, type, and intensity of AEs, and changes from baseline in safety laboratory tests, ECG findings, vital signs measurements, PFTs, and pulse oximetry. Immunogenicity will be assessed based on the incidence of infusion site reactions, ADA titers, changes in Jo-1 and ADA titers over time, as appropriate, as well as changes from baseline over time in immune-based laboratory tests, including, for example, tryptase, complement factors, and cytokines. Safety variables will be tabulated and presented for all patients who receive any amount of study drug and have follow-up safety data. Tabulations will be presented for safety data overall and separately for the parent and extension studies.

AEs will be coded using the current version of the Medical Dictionary for Regulatory Activities (MedDRA) for purposes of summarization. The overall incidence of AEs occurring during the study will be summarized by MedDRA system organ class and preferred term. The incidence of TEAEs also will be summarized by system organ class

and preferred term. For the purpose of analysis, a TEAE is defined as any AE that occurs after administration of the first dose of ATYR1940 through the 12-week posttreatment follow-up visit, or any event that is present at baseline, but worsens in intensity or is subsequently considered drug-related by the Investigator. Severe TEAEs, SAEs, and discontinuation rates of study therapy due to TEAEs also will be summarized.

Events that are considered related to treatment (possibly, likely, or definitely drug-related) will also be tabulated. A tabulation will also be provided that enumerates TEAEs by maximum severity. Deaths, SAEs, and TEAEs resulting in study discontinuation will be tabulated, if warranted by the data.

All AEs occurring on study will be listed in by-patient data listings.

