Any treatment-emergent adverse event	xx (xx.x)	xx (xx.x)	xx (xx.x)	xx (xx.x)
System Organ Class 1	xx (xx.x)	xx (xx.x)	xx (xx.x)	xx (xx.x)
Preferred Term 1	xx (xx.x)	xx (xx.x)	xx (xx.x)	xx (xx.x)
Preferred Term 2	xx (xx.x)	xx (xx.x)	xx (xx.x)	xx (xx.x)
...				
System Organ Class 2	xx (xx.x)	xx (xx.x)	xx (xx.x)	xx (xx.x)
Preferred Term 1	xx (xx.x)	xx (xx.x)	xx (xx.x)	xx (xx.x)
Preferred Term 2	xx (xx.x)	xx (xx.x)	xx (xx.x)	xx (xx.x)
...				
System Organ Class 3	xx (xx.x)	xx (xx.x)	xx (xx.x)	xx (xx.x)
...				

Note: FSHD=Facioscapulohumeral muscular dystrophy; LGMD2B=Limb-girdle muscular dystrophy 2B; EO-FSHD=Early Onset Facioscapulohumeral muscular dystrophy

Note: Adverse events are coded using MedDRA version 18.1. Only treatment-emergent adverse events are summarized. For each system organ class and preferred term, patients are included only once.

Note: Percentage based on the number of patients in the Safety population cumulative.

Source: Listing xx.x.xx, Dataset: [NAME], Program: xxxxxx.sas, Output: T_14_2_1_2_XXXXX.rtf, Generated on: DDMMYYYY HH:MM

Page x of y

Programming Note: Sort by decreasing frequency of "Total" column for both SOC and preferred term.

14.2.1.3 Related Treatment-Emergent Adverse Events by System Organ Class and Preferred Term (Safety Population Cumulative)

Programming Note: Repeat previous table 14.2.1.2. Add footnote: Note: "Related" defined as possibly, likely, or definitely.

14.2.1.4 Treatment-Emergent Adverse Events by System Organ Class, Preferred Term, and Maximum CTCAE Grade (Safety Population Cumulative)

System Organ Class Preferred Term	EO-FSHD (N = XX)					Total n (%)
	Grade 1 n (%)	Grade 2 n (%)	Grade 3 n (%)	Grade 4 n (%)	Grade 5 n (%)	
Parent and Current Studies Overall						
Any treatment-emergent adverse event	xx (xx.x)	xx (xx.x)	xx (xx.x)	xx (xx.x)	xx (xx.x)	xx (xx.x)
System Organ Class 1						
Preferred Term 1	xx (xx.x)	xx (xx.x)	xx (xx.x)	xx (xx.x)	xx (xx.x)	xx (xx.x)
Preferred Term 2	xx (xx.x)	xx (xx.x)	xx (xx.x)	xx (xx.x)	xx (xx.x)	xx (xx.x)
Preferred Term 3	xx (xx.x)	xx (xx.x)	xx (xx.x)	xx (xx.x)	xx (xx.x)	xx (xx.x)
Preferred Term 4	xx (xx.x)	xx (xx.x)	xx (xx.x)	xx (xx.x)	xx (xx.x)	xx (xx.x)
Preferred Term 5	xx (xx.x)	xx (xx.x)	xx (xx.x)	xx (xx.x)	xx (xx.x)	xx (xx.x)
...						
System Organ Class 2						
Preferred Term 1	xx (xx.x)	xx (xx.x)	xx (xx.x)	xx (xx.x)	xx (xx.x)	xx (xx.x)
Preferred Term 2	xx (xx.x)	xx (xx.x)	xx (xx.x)	xx (xx.x)	xx (xx.x)	xx (xx.x)

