Preferred Term 3	xx (xx.x)	xx (xx.x)	xx (xx.x)	xx (xx.x)	xx (xx.x)	xx (xx.x)
Preferred Term 4	xx (xx.x)	xx (xx.x)	xx (xx.x)	xx (xx.x)	xx (xx.x)	xx (xx.x)
Preferred Term 5	xx (xx.x)	xx (xx.x)	xx (xx.x)	xx (xx.x)	xx (xx.x)	xx (xx.x)
...						
System Organ Class 3						
...						

Note: FSHD=Facioscapulohumeral muscular dystrophy; LGMD2B=Limb-girdle muscular dystrophy 2B; EO-FSHD=Early Onset Facioscapulohumeral muscular dystrophy

Note: Adverse events are coded using MedDRA version 18.1 and graded using CTCAE v4.03. For each system organ class and preferred term, patients are included only once at the maximum severity.

Note: Percentage based on the number of patients in the Safety population Cumulative.

Source: Listing xx.x.xx, Dataset: [NAME], Program: xxxxxx.sas, Output: T_14_2_1_4_XXXXX.rtf, Generated on: DDMMYYYY HH:MM

Page x of y

Programming Note: Repeat page for each disease group (FSHD, EO-FSHD, and LGMD2B) and total. Sort by decreasing frequency of "Total" column for both SOC and preferred term. Preferred terms appearing in any group should be displayed in all groups (i.e., keep 0 rows in other groups).

14.2.1.5 Treatment-Emergent Adverse Events Leading to Study Medication Withdrawal by System Organ Class and Preferred Term (Safety Population Cumulative)

Programming Note: Repeat previous table 14.2.1.2, subsetting for TEAEs with action taken of study drug withdrawn. Replace first row header with: "Any TEAE with action taken of study drug withdrawn."

14.2.1.6 Serious Treatment-Emergent Adverse Events by System Organ Class and Preferred Term (Safety Population Cumulative)

Programming Note: Repeat previous table 14.2.1.2, subsetting for serious TEAEs. Replace first row header with: "Any serious TEAE."

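### The only TEAE-by-grade table (14.2.1.4) pools parent and extension data, so 006-only incidence by maximum grade is not tabulated

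*SAP*

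**What the plan says.** The first safety endpoint in Protocol 3.2.1 is "Incidence of TEAEs and serious adverse events (SAEs) overall and by intensity". Protocol 9.2.9 turns this into analysis commitments: "A tabulation will also be provided that enumerates TEAEs by maximum severity", and "Tabulations will be presented for safety data overall and separately for the parent and extension studies".

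SAP 9.0 sets a general rule: "Summary tables will be organized overall and by disease group, if applicable, for the two Safety populations". Those populations are Safety Population 006 (006 data only) and Safety Population Cumulative (the same patients, with parent and 006 data together). SAP 9.6.1 lists "TEAEs by MedDRA SOC, PT, and maximum CTCAE grade" among the planned summaries and does not limit it to pooled data. Its counting rule is that "patients with multiple events within a particular SOC or PT will be counted under the category of their most severe event".

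The shell that implements this is Table 14.2.1.4 in SAP Appendix 5, titled "Treatment-Emergent Adverse Events by System Organ Class, Preferred Term, and Maximum CTCAE Grade (Safety Population Cumulative". It has columns for Grades 1 to 5 and a total. Its only study block is the pooled one, and its programming note says "Repeat page for each disease group (FSHD, EO-FSHD, and LGMD2B) and total". Nothing in the shell or the note asks for a repeat by study.

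**The concern.** This is a long-term safety extension. The parent studies treated patients for 12 weeks, while 006 sets no maximum duration. A natural question for the tables is how severe the events were during extended dosing, as distinct from the first 12 weeks.

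The severity table is the one adverse event table that cannot answer it. Someone working from the summary tables can see how many patients had a given event in 006, and how many had a related or serious one, but not the grades of those events in 006. The shell also disagrees with the protocol's commitment to separate tabulations and with the SAP's own rule on the two populations. Programmers usually build from the shell, so the shell is likely to prevail unless it is corrected.

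**Working it through.** The plan gives no figure to reproduce, so the check is an inventory of outputs followed by a short piece of logic.

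**1. Study blocks in the seven adverse event shells (SAP Appendix 5)**

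| Table | Content | Pooled block | 006 block |
|---|---|---|---|
| 14.2.1.1 | Overall summary | yes | yes |
| 14.2.1.2 | SOC and PT | yes | yes |
| 14.2.1.3 | Related | inherited from 14.2.1.2 | inherited |
| 14.2.1.4 | SOC, PT and maximum grade | yes | **no** |
| 14.2.1.5 | Leading to drug withdrawal | inherited from 14.2.1.2 | inherited |
| 14.2.1.6 | Serious | inherited from 14.2.1.2 | inherited |
| 14.2.1.7 | PT | yes | yes |

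Three tables carry the 006 block and three inherit it: 3 + 3 = 6 of 7. The exception is the only table with grade columns.

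**2. Is 006 severity shown elsewhere?** SAP Appendix 4 lists no other TEAE table by grade. The 006 block of Table 14.2.1.1 has rows for serious and fatal TEAEs but none for grade. Listing 16.2.9 gives each event with its grade, TEAE flag and study. Listings 16.2.9.1 and 16.2.9.2 give grades for infusion-day events and for symptoms of infusion-related reactions. So 006 grades are available event by event, not as incidence.

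**3. What the pooled table says about 006.** Take one row of Table 14.2.1.4: a PT, a SOC, or the line for any TEAE. For patient *i*, let P be the highest parent-study grade in that row and E the highest 006 grade, with 0 for no event. The table shows M = max(P, E). Assume that every current-study TEAE is also in the pooled set. Then for any grade *g*:

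- number with M ≥ *g* = (number with E ≥ *g*) + (number with P ≥ *g* and E < *g*).

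The last term cannot be negative, so the pooled count at or above a grade is an upper bound on the 006 count. The excess is the number of patients whose grade *g* or higher came only from the parent period, and no planned table gives it. Table 14.2.1.2 gives the number of patients with any 006 event in the row, but without grade. For Grades 2 to 4, the tables therefore leave the 006 count anywhere from 0 to the smaller of the pooled count and that 006 total. Grade 5 is not in doubt, because everyone in the cumulative population went on to be dosed in 006.

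**4. Which rows are affected.** The once-only count applies within each SOC or PT.

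- Hypothetical patient A has Grade 3 headache in the parent study and Grade 1 nausea in 006. The headache row shows Grade 3, the nausea row still shows Grade 1, and the line for any TEAE shows Grade 3. The 006 grade is lost only in that last line.
- Hypothetical patient B has Grade 3 headache in the parent study and Grade 1 headache in 006. The headache row shows Grade 3 only, and the 006 event leaves no trace in the table.

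Replacement thus needs a recurring PT or SOC, or concerns the line for any TEAE. Separately, a PT seen only in the parent studies appears in the pooled table with nothing to show that it did not occur in 006.

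**The case against.** The strongest reply is that the endpoint is reported. Protocol 3.2.1 does not restrict it to 006-only data, Protocol 9.2.1 says parent and current data will be combined, and Table 14.2.1.4 is the tabulation by maximum severity that Protocol 9.2.9 asks for. With up to 24 patients, the 006 distribution can be worked out from Listing 16.2.9. All of this is correct, and it rules out a reading that someone might reach from the shell alone: that TEAE intensity is never reported for this study. What is missing is the split by period, which Protocol 9.2.9 requires in addition to the overall tabulation. A listing is not an incidence table.

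Other stronger readings also fail:

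- **That pooling conceals severe 006 events.** It does not. Pooling can only raise a patient's displayed grade in a row. A patient with a Grade 3 or higher TEAE in 006 still appears at Grade 3 or higher.
- **That each patient appears once in the whole table at the worst grade from either study.** The rule works row by row, as shown above.
- **That the SAP made an undeclared decision to drop the analysis.** SAP 1.1 is silent on it, but SAP 9.0 and 9.6.1 support producing it. The documents show a shell out of line with its own text, not a decision.
- **That serious events must also be tabulated by grade.** Protocol 9.2.9 specifies no such table. Serious TEAEs already enter Table 14.2.1.4 and are listed with grade in 16.2.9. An extra table would be a preference.

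The scope for distortion is also limited by eligibility. Protocol 5.2 excludes anyone who had a drug-related serious event of Grade 2 or higher in the parent study, so higher parent-study grades can come only from non-serious or unrelated events.

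**Conclusion.** The point holds as a conflict between a table shell and the text it implements. Followed as written, the shells give no 006-only incidence of TEAEs by maximum grade, for a first-listed safety endpoint in a study whose purpose is long-term safety. This is contrary to Protocol 9.2.9 and SAP 9.0.

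Its size is modest. One table of seven is affected. The underlying data are collected and listed, and the pooled counts at or above a grade err only upward for 006. The individual grade columns can err either way: a patient with Grade 3 in the parent study and Grade 1 in 006 drops out of the Grade 1 column for that row. How many patients would be affected cannot be estimated, because the documents give no grade distribution for either period. The upper-bound statement rests on every current-study TEAE also being in the pooled set. The point should be corrected because it costs almost nothing, not because a safety signal would otherwise be lost.

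**What to change.** Add a block headed *Current Study (ATYR1940-C-006) Overall* to Table 14.2.1.4, laid out as in Tables 14.2.1.2 and 14.2.1.7, and extend the programming note to repeat it by disease group and total. Derive the maximum grade in that block only from TEAEs that meet the current-study definition in SAP Section 6. That window opens at the parent-study Week 13 visit, so restricting the block to events with onset after the first 006 dose would create a second definition.

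Optionally, add a parent-study block to meet Protocol 9.2.9 in full. It should take only pooled TEAEs that do not meet the current-study definition, so that no event is counted in both blocks.

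The cost is one extra block (two with the option) in an existing program, plus a line of shell wording. No new data, table number or TEAE flag is needed for the 006 block.
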